1.8.3... Extended Therapy phase: Lenalidomide (Revlimid®) will be provided to research subjects for the duration the extened phase participation in this trial at no charge to them or their insurance providers. Lenalidomide will be provided in accordance with the RevAssist® program. Per standard RevAssist® requirements all physicians who prescribe lenalidomide for research subjects enrolled into this trial, and all research subjects enrolled into this trial, must be registered in and must comply with all requirements of Celgene's RevAssist® program. Prescriptions must be filled within 7 days. Only enough lenalidomide for one cycle of therapy will be supplied to the patient each cycle.

Patients will have a CBC prior to each new cycle of Revlimid®. Standard-of-care clinical visits with the principal investigator will take place every 3 months as long as the patient is participating in the Extended Therapy phase.

1.9 Response Criteria:

- 1.9.1 Complete Response (CR): Disappearance of all radiological and clinical evidence of tumor. The patient must be free of all tumor related symptoms for at least 4 weeks.
- 1.9.2 Partial Response (PR): 30% or greater decrease in the sum of the longest diameter of all measured lesions (or alternatively, ≥30% reduction of calculated tumor volumes) for at least 4 weeks.
- 1.9.3 Minor Response (MR): For tumors with a documented rate of progression (calculated as either the linear slope of calculated tumor volumes vs. time for the immediate year prior to initiating this study or as the slope of the logarithm of tumor volumes vs. time over the same interval), a decrease in the rate of progression by ≥50%.
- 1.9.4 Stable Disease (SD): No change or <30% decrease in the tumor volume (calculated as in 1.9.2) for at least 4 weeks.
- 1.9.5 Progressive disease (PD): Less than a 50% reduction in the rate of progression (see 1.9.3), an increase of >25% in the size of any measured lesion, or the appearance of new metastatic lesions.

Table 1: Schedule of Study Assessments

	Screening	Cycle	Cycle	Cycle	Cycle	Cycle	Cycle	Cycle	Cycle ,	Cycle	Cycle	ಲ	Cycle 12	Extension Phase	Extension Phase:	Extended Therapy
Procedure	prior to initiating	. H	79	т	খ	ŧn	9	r-	\$	٥,	2	Ħ	or Endin		Every 1 month	Phase: Every 3
	therapy												g Study			months
Complete medical history (prior treatment),	×															
Physical examination Kamofsky (clinic visit)	×	×	×	×	×	×	×	×	×	×	×	×	×			×

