enrolled patients. Aside from sedation and constipation, the drug was well tolerated with only one case of grade-2 peripheral-neuropathy after one year of treatment (30). A number of studies have suggested that there was no clearly defined threshold for thalidomide activity in responsive tumors, although in most studies responses were found at <800 mg daily, and that there was a wide range of variability in the occurrence toxicities. The large variety of solid tumors responsive to thalidomide validated the need to directly test this agent in any patients with solid tumors that lack effective alternative therapies.

There were no published trials of thalidomide in thyroid carcinomas; however, in a phase II trial of paclitaxel in anaplastic thyroid carcinoma, we noted that, after disease progression in one patient with a partial response to paclitaxel, an additional 6 month partial response was evoked with thalidomide, administered off protocol (12). Consequently, we performed a phase 2 clinical trial of thalidomide, administered as a single agent in rapidly progressive and radioiodine-unresponsive thyroid carcinoma, from 2001 and completed by 2003. Final publication of these results is pending; however, they were consistent with preliminary results published in late 2002. There was a greater than 50% response rate, ranging from partial responses to disease stabilization, with mean durability of response for at least 7 months (1). Unfortunately, there was significant toxicity with sedation, peripheral neuropathy and constipation. The availability of new derivatives of thalidomide with greater disease activity and fewer side effects provides an opportunity to gain greater therapeutic benefits.

3.4 REVLIMID®: Current clinical experience and preclinical studies:

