- 8.1.2 Radiological Studies: CT (without contrast for lung, otherwise with contra &/or MRI of evaluable disease.

8.2 Angiogenic Markers:

- 8.2.1 Proangiogenic cytokine: VEGF-A.
- 8.2.2 Antiangiogenic factors: sVEGFR-1, sVEGFR-2, and TSP-1.
- Evaluations during "Extended Therapy" phase: The following studies are obtained after the one-year protocol has concluded and the patient is maintaining a clinical response to REVLIMID® therapy and elects to continue to receive this drug and may receive REVLIMID through the RevAssist program. Note that these studies are performed as "standard-of-care" assessments that are appropriate for oncologic follow-up:
 - 8.3.1 Tumor Assessment (obtained at physician visits every 3 months):

 Tumor markers: Thyroglobulin Panel (TG & anti-TG Ab), TSH, free T4.

 Angiogenic Markers: Not done.

 Radiological Studies: CT (without contrast for lung; otherwise with contrast) of evaluable disease.

 Additional standard assessments: biochemistry panel and physical examination.
 - 8.3.2 Toxicity Monitoring (obtained every month while taking REVLIMID®): CL with differential/platelet count, and pregnancy test every 4 weeks if regular menstruation and every 2 weeks if irregular. All patients must continue to follow the birth control guidelines.
- 9.0 Response Criteria and Toxicity Assessment: Overall responses will be assessed as described in Figure 4, below. These assessments are adapted from RECIST Criteria (referenced in Fig. 4).

9.1 Parameters of Response:

- 9.1.1 Complete Response (CR): Disappearance of all radiological and clinical evidence of tumor. The patient must be free of all tumor related symptoms for at least 4 weeks.
- 9.1.2 Partial Response (PR): 30% or greater decrease in the sum of the longest diameter of all measured lesions (or alternatively, ≥30% reduction of calculated tumor volumes) for at least 4 weeks.
- 9.1.3 Minor Response (MR): For tumors with a documented rate of progression (calculated as either the linear slope of calculated tumor volumes vs. time for the immediate year prior to initiating this study or as the slope of the logarithm of CONFIDENTIAL

tumor volumes vs. time over the same interval), a decrease in the rate of progression by ≥50%.

- 9.1.4 Stable Disease (SD): No change or <30% decrease in the tumor volume (calculated as in 9.1.2) for at least 4 weeks.

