- 9.1.5 Progressive disease (PD): Less than a 50% reduction in the rate of progression (see 9.1.3), an increase of >20% in the size of target lesions, or the appearance of new metastatic lesions.

Figure 4. Overall responses for all possible combinations of tumor responses in target and non-target lesions with or without the appearance of new lesions* (Adapted from Therasse P, Arbuck SG, Eisenhauer EA, Wanders J, Kaplan RS, Rubinstein L, Verweij J, Van Glabbeke M, van Oosterom AT, Christian MC, Gwyther SG 2000 New guidelines to evaluate the response to treatment in solid tumors. European Organization for Research and Treatment of Cancer, National Cancer Institute of the United States, National Cancer Institute of Canada. J Natl Cancer Inst 92:205-16)

Target lesions	Non-target lesions	New lesions	Overall response
CR.	CR	No	CR
CR.	Incomplete response/MR/SD	No	PR
PR.	Non-PD	No	PR.
MR	Non-PD	No	MR
SD	Non-PD	No	SD
PD	Any	Yes or no	PD
	PD	Yes or no	PD
Any Any	Any	Yes	PD + 1.1a disease

^{*}CR= complete response; PR= partial response; MR= minor response; SD= stable disease; and PD= progressive disease.

9.2 Toxicity Assessment: This will be performed at intervals defined in section 7.0 using criteria defined in appendices A, B, & C.

10.0 Criteria for Discontinuing Therapy:

- 10.1 Progressive Disease is an indication to discontinue therapy.
- Adverse event(s) that, in the judgment of the Investigator, may cause severe or permanent harm or which rule out continuation of the study drug.
- 10.3 Non-compliance by the patient with protocol requirements.
- 10.4 Patient desire to discontinue therapy.
- 10.5 Evidence of pregnancy.

- 10.6 ... Withdrawal of consent.
- 10.7 Lost to follow-up.
- 10.8 Death

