- 11.0 Statistical Parameters: A two-stage design will be used, as described by Gehan (4), which entails the evaluation of 14 patients to determine whether there is at least one patient responsive to this treatment. Would no responders be found within 4 28-day cycles after initiating each of the 14 patients on the study drug, the study will end at that time. In the presence of at least one responder, the trial is planned to continue, accruing an additional 11 patients or sufficient patients to determine a 95% confidence interval for the true response rate. Thus, a total of 14 patients will be enrolled if there are no responders; however, up to 25 patients will be enrolled if there are responders in the initial group. Response rates of 65% have been noted in prior studies using the parent compound, thalidomide (1). Based on such activity, we anticipate that the probability of observing 'no responses' for this treatment regimen in 14 subjects is less than 4.0 x 10⁻⁷. In essence, there is very low probability that this study will not move into the second phase given the levels of tumor activity reported previously for this treatment.
- Protocol Management and Data Collection: All data will be collected and entered into the study database by the Nursing Staff of the University of Kentucky Clinical Research Organization (UK-CRO), Drs. [name] and [name], and the research support staff of the University of Kentucky Thyroid Oncology Program. Clinical decisions regarding study subjects, as well as protocol decisions, will be the responsibility of the Principal Investigator. The Markey Cancer Center Data and Safety Monitoring System (DSMS) will be used to monitor this study (see section 13.6).

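### Section 11.0 does not say which response categories make a responder, its 65% benchmark comes from a trial whose responses ran to disease stabilization, and the PR, MR and PD rules beneath it conflict

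*Combined protocol and SAP*

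**What the plan says.** Section 11.0, repeated in the statistical paragraph of the Protocol Abstract (section 1.0), sets a Gehan two-stage design. Fourteen patients are treated first: "Would no responders be found within 4 28-day cycles after initiating each of the 14 patients on the study drug, the study will end". With at least one responder, 11 more are added, up to 25, to give a 95% confidence interval for the true response rate. The support is "Response rates of 65% have been noted in prior studies using the parent compound, thalidomide (1", from which the plan puts the probability of no responses in 14 below 4.0 x 10⁻⁷. Section 3.3, citing the same reference, reports of the thalidomide trial: "There was a greater than 50% response rate, ranging from partial responses to disease stabilization".

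Objective 4.1 names tumor response and response duration. Section 9.1 and Figure 4 define CR, PR, MR, SD and PD, but not which of them is a response. The rules are:

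- **PR (9.1.2):** "30% or greater decrease in the sum of the longest diameter of all measured lesions (or alternatively, ≥30% reduction of calculated tumor volumes".
- **MR (9.1.3):** growth slowed by at least half. The speed of growth is "calculated as either the linear slope of calculated tumor volumes vs. time for the immediate year prior to initiating this study"; log volume may be used in place of volume.
- **SD (9.1.4):** "No change or <30% decrease in the tumor volume".
- **PD (9.1.5):** "Less than a 50% reduction in the rate of progression (see 9.1.3), an increase of >20% in the size of target lesions". New lesions also count. The abstract (1.9.5) has instead "an increase of >25% in the size of any measured lesion".

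On stopping drug, 5.2.2 treats until progression as defined in section 9.0, and 10.1 makes PD a reason to stop. The Treatment Plan paragraph of the abstract continues treatment unless growth is at or above the baseline-year rate.

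**The concern.** The go/no-go decision and the headline estimate share a numerator that the plan does not define, and its cues point two ways. Section 9.0 is adapted from RECIST, which suggests CR+PR. The benchmark, and the lenalidomide melanoma result in 3.4 (1 PR and 6 stabilizations counted as seven clinical responses), suggest that stabilization counts. In a single-arm trial the choice could then be made after the scans are read. The assurance that the study will almost certainly reach stage 2 holds only under the broader meaning.

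The category rules add a second layer. The PR measure can change a CR+PR count. The slope scale and the PD rules decide who stays on drug. They also move response duration, a primary objective, if it ends at PD, which sections 9 and 11 do not state.

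**Working it through.** **1. The plan's figure.** P(0 of 14) = (1 − p)¹⁴. At p = 0.65, 0.35¹⁴ = 4.14 x 10⁻⁷. The stated bound of 4.0 x 10⁻⁷ is missed only by rounding (it needs p of about 0.651).

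**2. The same figure for CR+PR.** The documents give no CR+PR rate for thyroid cancer, so these rates are assumptions:

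| Assumed CR+PR rate | P(0 of 14) |
|---|---|
| 20% | 0.80¹⁴ = 4.4% |
| 10% | 0.90¹⁴ = 22.9% |
| 5% | 0.95¹⁴ = 48.8% |

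The background data in other tumors show how far the definition alone can move the result:

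- Melanoma on lenalidomide (3.4): PR only, 1/13, gives (12/13)¹⁴ = 0.33; PR+SD, 7/13, gives (6/13)¹⁴ = 2.0 x 10⁻⁵.
- Glioma on thalidomide (3.3): PR only, 2/39, gives (37/39)¹⁴ = 0.48; PR+MR+SD, 16/39, gives (23/39)¹⁴ = 6 x 10⁻⁴.

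**3. The two PR tests.** Under uniform shrinkage, a 30% fall in diameter is a volume fall of 1 − 0.7³ = 65.7%. A 30% fall in volume is a diameter fall of 1 − 0.7^(1/3) = 11.2%. A volume loss from 30% to just under 65.7% is PR by volume and not by diameter.

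**4. Slope scale.** Let g be the baseline-year rise in volume and t = 112/365.25 = 0.307 years (16 weeks). Growth is measured from the volume at treatment start, (1+g) times the volume a year earlier. The growth at which the rate is exactly halved is:

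- linear: 0.5 × g/(1+g) × t
- log: exp(0.5 × ln(1+g) × t) − 1

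The entry minimum (inclusion criterion 4, taken over a full year) is g = 0.3. The doubling tumor, g = 1, is an assumption.

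| g | Linear limit | Log limit |
|---|---|---|
| 0.3 | 3.5% | 4.1% |
| 1 | 7.7% | 11.2% |

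Growth between the two limits is PD on the linear scale and meets MR on the log scale. The band is narrow at the entry minimum and wider for a fast tumor.

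**5. Stop rule.** The abstract's limit is the full baseline rate: g/(1+g) × t (linear) or exp(ln(1+g) × t) − 1 (log). Any rate reduction above zero and below 50% is PD and stops drug under 9.1.5, 5.2.2 and 10.1, but continues under the abstract. At 16 weeks the conflicting range of volume growth is:

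| g | Linear | Log |
|---|---|---|
| 0.3 | 3.5% to 7.1% | 4.1% to 8.4% |
| 1 | 7.7% to 15.3% | 11.2% to 23.7% |

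**6. PD size limit.** A target-lesion increase above 20% and up to 25% is PD under 9.1.5 but not under the size clause of 1.9.5.

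**7. MR against size PD.** Suppose a tumor grew 30% in two months (eligible; assumed here) and its rate is exactly halved on drug. Its 16-week volume growth is 0.5 × (0.3/1.3) × 6 × t = 21.2% (linear) or exp(0.5 × ln 1.3 × 6 × t) − 1 = 27.3% (log). If size means volume, that meets MR and also exceeds the 20% PD limit. Nothing says which prevails.

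**The case against.** Several points against a broader criticism are sound.

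- **Abstract against body.** The 25% limit and the looser continuation rule sit in the Protocol Abstract, while 5.2.2 points expressly to section 9.0 and 10.1 agrees. Section 9 is the natural governing text. There is no precedence clause, so the conflict needs correcting, but as a consistency edit.
- **Either test may suffice for PR.** The wording of 9.1.2 can be read that way. Under uniform shrinkage, anyone who meets the diameter test also meets the volume test, so that reading gives one answer. Section 6.2.3 and the Table 1 footnotes make volume the operational measure. The reading is reasonable but not stated.
- **Sample size.** The plan does not derive 14 or 25 from the 65%. At a 20% CR+PR rate, 0.80¹⁴ = 4.4%, so 14 patients still serve as a first stage.
- **The benchmark's make-up.** It lies in a source outside these documents. Section 3.3 reports above 50% rather than 65%; that both describe one trial is inferred from the shared reference.

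A reader might also infer that SD is an empty category, because every patient had growth at entry and no change is therefore a 100% fall in rate. The documents do not support that. MR requires a documented rate, and entry documents growth per patient, whereas Figure 4 separates target from non-target lesions; some lesions may have no computable slope. The MR/SD overlap is real, but it moves the responder count only if MR counts and SD does not, a definition that the documents nowhere propose.

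**Conclusion.** The concern stands on two levels. First, the responder behind the stage-1 rule and the 95% interval is undefined, and the stated probability of no responses does not carry over to CR+PR. There it is 4.4% to 49% over assumed rates of 20% to 5%. Second, the PR measure, the slope scale, the PD size limit and the continuation rule each admit two answers for the same patient.

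Two stronger conclusions should not be drawn. One is that the primary endpoint cannot be scored under any reading. Under CR+PR, the MR/SD and MR/PD conflicts do not directly change the responder count, and only the PR measure does. Under CR+PR+MR+SD, the MR/SD overlap and the PR measure drop out, leaving the slope scale and the PD rules. The other is that the trial is likely to stop early: the 5% to 20% rates are assumptions, and the melanoma and glioma data only illustrate.

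The volume and diameter equivalents assume uniform shrinkage, and the wider slope bands assume a doubling tumor.

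**What to change.** 1. **Responder.** In section 11.0 and the abstract, define responder as CR+PR for both the stage-1 rule and the 95% interval. Report CR+PR+MR+SD separately as disease control, for comparison with thalidomide. Delete or restate the 65%-based probability. If stabilization is meant to count, state that responders are CR+PR+MR+SD and report CR+PR separately. Do not use CR+PR+MR without SD: where MR and SD are told apart by whether the tumor is still growing, that would credit a slowly growing tumor over one that shrank by less than 30%.
2. **PR.** Score it on one measure, volume being the one that 6.2.3 sets up, or state that meeting either test suffices.
3. **Slope.** Fix one scale for all patients before on-treatment scans are read, and report the other as a sensitivity analysis.
4. **PD.** Make 9.1.5 the single definition and say whether size means diameter or volume. State that PD by size or new lesion overrides MR. Align 1.9.5 and the abstract's continuation rule to it, and state that response duration ends at that PD.
5. **MR/SD.** Separate the two as a secondary consistency edit; it does not move the count under either definition in item 1.

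The cost is wording only: no added scans or patients, since both slopes come from the same volumes. The downside is that under CR+PR the headline rate may be lower, it is no longer directly comparable with the 65% figure, and stopping at stage 1 becomes a real possibility.
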